## Other Secondary Endpoints

- To explore pharmacodynamic effects of DACOGEN with respect to DNA hypomethylation status and gene expression
- To explore predictive markers for response to DACOGEN.
- Levels of DACOGEN in the CSF if samples are collected as part of other required medical care.

### 9.2.3. Pharmacokinetics Evaluations

Serial whole blood samples (0.5 mL each) for PK will be obtained on Day 5 of Cycle 1 as indicated in the Time and Events Schedule for determination of decitabine plasma concentrations. Blood samples for pharmacokinetic analyses should not be collected through the same line through which decitabine is infused. Pharmacokinetics samples can be taken via a central line if the decitabine infusion is given peripherally. If attempts to place a peripheral line are unsuccessful, and decitabine is given through a single lumen central line, consider to only collect pre-infusion and post-infusion PK samples. The exact dates and times of blood sample collection must be recorded at minimum on the laboratory requisition forms.

In subjects whose course of routine treatment includes sampling of CSF, a portion of that sample may be assessed for decitabine drug levels.

An interim PK analysis will be performed after the completion of Phase 1 PK assessments. Based on the results of the interim PK analysis of Phase 1, the collection timepoints of PK samples may be optimized and if possible reduced for the Phase 2 portion of the study.

### 9.2.4. Analytical Procedures

#### Pharmacokinetics

Plasma samples will be analyzed to determine concentrations of decitabine using a validated, specific, and sensitive liquid chromatography coupled to tandem mass spectrometry (LC-MS/MS) method under the supervision of the sponsor's Bioanalytical Laboratory Department of Bioanalysis.

PK sample collection, processing, storage, and shipping instructions for these PK blood samples are presented in the PK lab manual provided by the sponsor or sponsor's representative.

If required, some plasma samples may be analyzed to document the presence of circulating metabolites using a qualified research method.

### 9.2.5. Pharmacokinetic Parameters

PK analysis will be the responsibility of the Sponsor in accordance with the sponsor's current Clinical Pharmacokinetics Guideline. The following PK parameters for decitabine will be calculated on Day 5 of Cycle 1 by non-compartmental methods using WinNonlin Version 5.0 or higher:

$C_{max}$	maximum plasma concentration
$t_{max}$	time to reach the maximum plasma concentration
$AUC_{last}$	area under the plasma concentration-time curve from time 0 to the time of the last quantifiable concentration
$AUC_{\tau}$	area under the plasma concentration-time curve from time 0 to 24 hr
$t_{1/2, \lambda}$	elimination half-life associated with the terminal slope ( $\lambda_z$ ) of the semilogarithmic drug concentration-time curve, calculated as $0.693/\lambda_z$
$\lambda_z$	first-order rate constant associated with the terminal portion of the curve, determined as the negative slope of the terminal log-linear phase of the drug concentration-time curve
CL	total clearance of drug after IV administration, calculated as: dose/ $AUC_{\tau}$
$VD_{ss}$	volume of distribution at steady state, calculated as $\lambda_z / CL$

Actual blood sampling times relative to study medication administration will be used for the analysis. Additional PK parameters may be determined as appropriate.

Cytarabine PK parameters will not be evaluated. They are already well described in this population at the doses planned. Since decitabine has a terminal half-life of  $0.51 \pm 0.31$  hour (DACOGEN package insert) and two full days will pass from the last dose of decitabine to the first of cytarabine, no drug-drug interaction is expected.

Based on the individual plasma concentration-time data, using the actual dose taken and the actual sampling times, pharmacokinetic parameters and exposure information of decitabine will be derived using population pharmacokinetic modeling. Baseline covariates (eg, body weight, age, sex, creatinine clearance, race) may be included in the model, if relevant.

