- k) Bone marrow aspirates will be performed at the end of Cycle 1 of sequential treatment (Day 28 or within 8 days of the start of the next cycle), the end of Cycle 2 if the subject did not achieve a CR at the end on Cycle 1, at the end of sequential treatment, or at any time disease progression is suspected. For Phase 1, bone marrow aspirates at end of Cycle 1 should be obtained no later than Day 42 in order to determine potential dose limiting toxicity. If available, a portion of the bone marrow aspirate collected at Screening and at end of the first Cycle will be used for DNA methylation/ mutation assessment, gene expression, and micro RNA analyses.
- l) Results should be recorded if a bone marrow aspirate is obtained as part of standard clinical care.

- m) Response assessment is performed at time at which bone marrow aspirate is obtained.
- n) Hemoglobin, platelet count, white blood cell count, absolute neutrophil count (ANC), peripheral blast count
- o) First cycle only
- p) For the DACOGEN continuation period, hematology samples are obtained on Day 1 of each cycle prior to drug administration.
- q) To include  $\text{Na}^+$ ,  $\text{K}^+$ , creatinine, aspartate aminotransferase (AST), alanine aminotransferase (ALT), total bilirubin, serum uric acid
- r) 0.5 mL whole blood to be obtained (blood should not be collected through the same line through which decitabine is infused, see Section 9.2.3) at; pre-infusion, 0.5 h during infusion, end of infusion, +5 min, +0.5h, +1h, and +2h after end infusion. Samples will be collected from Phase 1 and Phase 2 subjects. 0.5 ml of cerebrospinal fluid (CSF) will be collected for PK analysis when/if CSF is obtained as part of routine medical care except at screening.
- s) Whole blood sample (2 mL) for DNA methylation pattern and DNA mutation determination at screening, prior to drug administration on Day, 8, and at the end of Cycle 1. This sample may also be used for gene expression and micro RNA analysis in the event only one biomarker blood sample can be drawn.
- t) Whole blood (2.5 mL) for gene expression profiling and micro RNA analysis at screening, prior to drug administration on Day 8, and at the end of Cycle 1.

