#### 1.1.4.1. Human Pharmacokinetic Studies

The population PK parameters of decitabine in adults were pooled from 3 clinical studies (DACO-017 [n=11], DACO-020 [n=11] and DACO- 016 [n=23]) utilizing the 5-Day regimen (20 mg/m^2 IV infusion for 1-hour x 5 days every 4 weeks) and 1 study, DACO-018 (n=12), utilizing the 3-Day regimen (15 mg/m^2 IV infusion over 3-hours every 8 hours x 3 days every 6 weeks) in MDS or AML patients. For the 5-Day regimen, decitabine PK was evaluated on the fifth day of the first treatment cycle. Total dose per cycle was 100 mg/m^2. For the 3-Day regimen, decitabine PK was evaluated after the first dose of each dosing day of the first treatment cycle. Total dose per cycle was 135 mg/m^2.

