#### Distribution

The PK of decitabine following intravenous administration as a 1-hour (5-Day regimen) or 3-hour (3-Day regimen) infusion was described by a linear two-compartment model, characterized by rapid elimination of the drug from the central compartment and by relatively slow distribution from the peripheral compartment. For a typical patient (weight 70 kg/body surface area 1.73 m^2) the decitabine PK parameters are listed in [Table 1](#) below.

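### Non-compartmental terminal half-life from samples ending 2 h after infusion can be biased downward by an amount the protocol cannot fix, and the VDss formula is dimensionally wrong

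*Combined protocol and SAP*

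**What the plan says.** Section 9.2.5 lists Cmax, tmax, two AUCs, terminal half-life, lambda_z, CL and VDss, all of which "will be calculated on Day 5 of Cycle 1 by non-compartmental methods using WinNonlin Version 5.0 or higher". Lambda_z is "determined as the negative slope of the terminal log-linear phase of the drug concentration-time curve", half-life is 0.693/lambda_z, CL is dose/AUC_tau, and VDss is lambda_z divided by CL. No rule is given for which points enter the slope or how long they must span. The section refers to a sponsor pharmacokinetics guideline that is not part of the documents.

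Footnote r of the Time and Events Schedule sets the samples at "pre-infusion, 0.5 h during infusion, end of infusion, +5 min, +0.5h, +1h, and +2h after end infusion".

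For adults, Section 1.1.4.1 says the PK was "described by a linear two-compartment model, characterized by rapid elimination of the drug from the central compartment". Table 1 (5-Day regimen) gives a half-life of 68.2 min (95% CI 54.2 to 79.6). Section 9.2.5 gives another adult figure: "Since decitabine has a terminal half-life of" 0.51 ± 0.31 h, taken from the package insert.

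Sections 9.2.5, 9.3 and 11.5 also plan a population PK analysis, and Section 9.3 says the adult model will be updated with these data. Section 11.5 plans summaries of half-life, CL and V when available. Nothing says which estimate of half-life or volume governs.

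**The concern.** A log-linear slope estimates the terminal rate only if the points lie beyond the distribution phase. With a 68.2 min half-life, +0.5 to +2 h covers 90/68.2 = 1.3 half-lives, and the whole post-infusion window covers 120/68.2 = 1.8. If distribution is not finished by +0.5 h, the slope mixes the two phases and the half-life comes out too short.

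The pediatric half-life, and any volume built on lambda_z, could then differ from Table 1 because of the sampling window and not because of age. Section 3.2 states that no PK difference between children and adults is expected, so readers will make that comparison. Because the protocol carries two adult half-lives, a result in the thirties of minutes could be read as contradicting one and agreeing with the other.

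**Working it through.** **Inputs.** Table 1, 5-Day column: Cmax 107 ng/mL, cumulative AUC 580 ng·h/mL, half-life 68.2 min, Vdss 116 L, CL 298 L/h. Section 1.1.4.1: 20 mg/m² as an "IV infusion for 1-hour x 5 days every 4 weeks"; typical BSA 1.73 m². Sampling times: footnote r.

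**Reproducing Table 1.** Dose = 20 × 1.73 = 34.6 mg. AUC per infusion = 34.6/298 = 116.1 ng·h/mL. Over 5 days this is 580.5, against 580 stated.

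**Two-compartment profile.** Constraints: k10 = CL/V1; V1(1 + k12/k21) = 116 L; αβ = k10·k21; α + β = k10 + k12 + k21; β = 0.693/(68.2/60) = 0.610/h; concentration at end of infusion = 107 ng/mL. Solution: V1 = 65.5 L, k10 = 4.55/h, k12 = 0.533/h, k21 = 0.692/h, α = 5.16/h (distribution half-life 8.1 min).

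Concentrations (ng/mL): end of infusion 107; +5 min 71.7; +0.5 h 12.84; +1 h 4.467; +2 h 2.120.

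**Three-point slope (+0.5, +1, +2 h).** The logs are 2.553, 1.497 and 0.751. Sxx = 1.1667 and Sxy = −1.325, so lambda_z = 1.136/h and half-life = 0.693/1.136 = 0.61 h = 36.6 min, or 54% of 68.2. With the +5 min point it is 24.3 min; with the end-of-infusion point as well, 21.4 min. The last two points alone give 55.8 min.

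**Sensitivity to central volume**, holding CL, Vss and the 68.2 min half-life:

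| V1 (L) | Implied Cmax (ng/mL) | Half-life, +0.5 to +2 h (min) | Half-life, +5 min to +2 h (min) |
|---|---|---|---|
| 20 | 102.7 | 68.1 | 40.8 |
| 30 | 103.7 | 66.6 | 34.6 |
| 40 | 104.6 | 60.2 | 31.0 |
| 50 | 105.6 | 50.4 | 28.1 |
| 60 | 106.5 | 41.0 | 25.6 |
| 65.5 | 107.0 | 36.7 | 24.4 |
| 70 | 107.3 | 33.5 | 23.4 |
| 80 | 107.8 | 27.9 | 21.5 |
| 90 | 108.0 | 23.5 | 19.8 |

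Every implied Cmax lies well inside Table 1's interval (88.5 to 129). Rounding of 107 alone (106.5 to 107.5) moves the three-point answer from 41.5 to 31.6 min. At 107.5 there is also a second root, with V1 = 111.3 L (nearly all of Vss), which gives 17.1 min; I leave it outside the range quoted.

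Varying CL, Vdss and half-life over their intervals, with Cmax scaled to CL, the ratio to the true half-life runs from 0.53 to 1.00 wherever the model can be solved. In no case tried did the fit exceed the true value.

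**3-Day column as a cross-check.** Rate = 15 × 1.73/3 = 8.65 mg/h, CL 201 L/h, Vdss 49.6 L, half-life 67.5 min, Cmax 42.25 to 42.35 ng/mL. This implies V1 of about 15 to 20 L and a three-point half-life of about 64 to 67 min, which is almost unbiased.

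**Effect on clearance.** At V1 = 65.5 L the AUC tail beyond +2 h is 2.12/0.610 = 3.5 ng·h/mL at the true slope, or 3.5/116.1 = 3.0% of the total, and 2.12/1.136 = 1.9 at the biased slope. With linear trapezoids on the planned samples, CL is 310.6 L/h with the true slope and 315.2 with the biased one, a 1.5% change. The gap between 310.6 and 298 comes from coarse trapezoids, not from lambda_z.

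**VDss.** (1/h)/(L/h) = 1/L, so lambda_z/CL is not a volume. Inverted, CL/lambda_z is 298/0.610 = 489 L at the true slope and 298/1.136 = 262 L at the biased slope. Neither is Table 1's Vdss of 116 L.

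**Two adult half-lives.** 0.51 × 60 = 30.6 min, below Table 1's lower limit of 54.2 min.

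**The case against.** The size of the bias is not established. The 37 min figure needs V1 = 65.5 L, which appears nowhere in the documents and follows only from taking Cmax as exactly 107. Lowering Cmax by about 4%, to 103, removes the effect, and the 3-Day column of the same table points to almost none. This stands: a reader might infer that the half-life will be about halved, and the documents do not support that.

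A reader might also infer that children would appear to eliminate decitabine faster. That is not supported either. Clearance hardly moves, and beside the protocol's own 30.6 min a 37 min result would look slightly slow. Nor is the primary PK endpoint at risk: Sections 2.1 and 9.2.2 name Cmax, AUC, tmax and Cl, not half-life. Section 3.2 is design rationale, and no test against adult half-life is planned.

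Some protection may exist. The sponsor guideline may contain acceptance rules for lambda_z, Section 11.5 excludes data inadequate for parameter calculation, and the three-point fit has an adjusted R² of only 0.837, which a fit-quality rule might flag. A rule based on span alone would not be reliable, because the biased estimate makes the span look longer (90/36.6 = 2.5 half-lives against a true 1.3).

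The population model already offers a like-for-like link to adults. That makes the remedy cheap but does not remove the need for it: the non-compartmental half-life remains a listed parameter, and no text gives the model precedence.

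**Conclusion.** The point holds as a specification weakness in the terminal-phase parameters. Under the protocol's two-compartment adult description, a half-life fitted to +0.5 to +2 h is biased downward or at best unbiased: about 37 min at Table 1 point values, with a range of about 23 to 68 min for central volumes of 20 to 90 L. Including the +5 min sample, which no text prevents, gives about 20 to 41 min, below Table 1's lower limit throughout. The direction is firm within this model; the size is not. AUC and CL change by about 1 to 2%, so the named primary PK parameters stand.

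Two faults do not depend on the central volume: the VDss formula is dimensionally wrong, and the two adult half-lives disagree.

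Assumptions: Table 1 describes one noise-free typical adult; the regression is unweighted; at least three points are used; and no quantification limit intervenes (none is stated). How far the adult profile carries over to children is unknown.

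**What to change.** In Sections 9.2.5 and 11.5, state that terminal half-life, lambda_z and volumes, for reporting and for comparison with adults, come from the population PK model already planned. Keep Cmax, tmax, AUC and CL as non-compartmental outputs, with the extrapolated percentage of AUC shown.

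Alternatively, keep a non-compartmental half-life but label it as apparent over the sampled window, write down the point-selection rule, and compare it only with adult values computed over the same window.

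In either case, correct or drop the VDss formula (inverting it does not give Vss), and reconcile 68.2 min with 0.51 h.

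This changes wording only: no added samples and no change to the primary PK parameters. It is best settled before the interim PK analysis in Section 9.2.3, which may lead to fewer sampling times in Phase 2. The cost is that half-life and volumes would come from the separate population PK report.

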### 9.3. Pharmacokinetic/Pharmacodynamic Evaluations

Decitabine plasma concentration-time models data will also be analyzed using a population PK approach (non-linear mixed effect models) to establish decitabine PK parameters (eg, clearance and volume of distribution). The population PK model proposed for the adult population will be updated with the data obtained in this patient population. Data from this study may be combined with data from other studies to perform the population PK analysis.

Analyses comparing PK parameters of  $C_{max}$  and AUC with PD endpoints of DNA methylation and gene expression profiling may be undertaken to explore any potential relationships.

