### **11.5. Pharmacokinetic Analyses**

Population PK analysis of plasma concentration-time data of decitabine will be performed using nonlinear mixed-effects modeling. Data may be combined with those of other selected studies to support a relevant structural model. Available baseline subject characteristics (demographics, laboratory variables, genotypes, race, etc.) will be tested as potential covariates affecting PK parameters. Details will be given in a population PK analysis plan and the results of the population PK analysis will be presented in a separate report.

A snapshot date for PK samples to be analyzed will be defined, if required. Samples collected before this date will be analyzed for decitabine and included in the population PK analysis. Samples collected after the snapshot date will be analyzed at a later date, and may be included in a population PK re-analysis when they become available after database lock.

Data will be listed for all subjects with available plasma concentrations per treatment group. Subjects will be excluded from the PK analysis if their data do not allow for accurate assessment of the PK (eg, incomplete administration of the study drug; missing information of dosing and sampling times; concentration data not sufficient for PK parameter calculation).

All concentrations below the lowest quantifiable concentration or missing data will be labeled as such in the concentration database. All subjects and samples excluded from the analysis will be clearly documented in the study report.

For each treatment group, descriptive statistics, including arithmetic mean, SD, coefficient of variation, median, minimum, and maximum will be calculated for all individual derived PK parameters including exposure information of decitabine.

All plasma concentrations below the lowest quantifiable concentration or missing data will be labeled as such in the concentration data presentations or SAS dataset. Concentrations below the lower quantifiable concentration will be treated as zero in the summary statistics. All subjects and samples excluded from the analysis will be clearly documented in the Clinical Study Report.

Descriptive statistics will be used to summarize decitabine serum concentrations at each sampling time point and PK parameters of decitabine:  $C_{\min}$  and  $C_{\max}$ . Other PK parameters, including but not limited to  $AUC_{(t1-t2)}$ ,  $t_{1/2}$ , CL, and V, when available, will also be summarized.

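### Section 9.2.5 defines steady-state volume as lambda_z/CL, which is a reciprocal volume; it should read CL × MRT, or be relabelled Vz = CL/lambda_z

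*Combined protocol and SAP*

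**What the plan says.** Section 9.2.5 says that a list of decitabine parameters will be calculated on Day 5 of Cycle 1 by non-compartmental methods. Three entries matter here:

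- lambda_z is a first-order rate constant, the negative slope of the terminal log-linear phase, with half-life given as 0.693/lambda_z.
- CL is total clearance, dose divided by AUC over the 24-hour interval.
- VDss is "volume of distribution at steady state, calculated as $\lambda_z / CL".

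No MRT, AUMC or AUC to infinity is listed, although the section allows additional parameters. It also says the analysis will be done "in accordance with the sponsor's current Clinical Pharmacokinetics Guideline"; that guideline is not part of the documents.

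No other section gives a formula for the volume. Section 11.5 says only that "CL, and V, when available, will also be summarized". Section 1.1.4.1 says decitabine PK after infusion "was described by a linear two-compartment model, characterized by rapid elimination of the drug from the central compartment", and Table 1 there reports Vdss in litres: 116 L (95% CI 84.1–153) for the 5-day regimen and 49.6 L for the 3-day regimen.

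**The concern.** The printed rule fails a unit check: a rate constant divided by a clearance is one over a volume. Following it literally yields a number that cannot be reported in litres or compared with Table 1.

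The natural repair, inverting the fraction, carries a second problem. CL/lambda_z is the terminal-phase volume. It equals the steady-state volume only when disposition is one-compartment, and the protocol describes two compartments. The label therefore points to one volume and the inverted formula to another, and the bare V in Section 11.5 does not say which is wanted. A programmer who silently inverts the fraction and keeps the label could report a pediatric VDss that is not the same quantity as the adult Vdss in Table 1.

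**Working it through.** **1. Units, from Section 9.2.5 alone.** lambda_z is in 1/h and CL in L/h, so lambda_z/CL = (1/h)/(L/h) = 1/L. This step needs no figures.

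**2. Check that Table 1 is internally consistent.** The typical patient has a body surface area of 1.73 m². For the 5-day regimen the cumulative dose is 5 × 20 × 1.73 = 173 mg. With CL 298 L/h, AUC = 173/298 = 0.5805 mg·h/L = 580.5 ng·h/mL, against 580 printed. The CL value can be used.

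**3. Try to recover Table 1's Vdss from the printed formula and from its inverse.**

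| | 5-day | 3-day |
|---|---|---|
| CL (L/h) | 298 | 201 |
| t½ (min) | 68.2 | 67.5 |
| lambda_z = 0.693/(t½ in h) | 0.610 /h | 0.616 /h |
| lambda_z/CL, as printed | 0.00205 per L | 0.00306 per L |
| CL/lambda_z (Vz) | 489 L | 326 L |
| Vdss stated in Table 1 | 116 L | 49.6 L |
| Vz ÷ Vdss | 4.2 | 6.6 |

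Neither form reproduces Vdss. Moving CL and t½ to the ends of their 5-day confidence intervals gives Vz from 325 to 687 L, all above the Vdss interval of 84.1–153 L.

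**4. Check the proposed formula.** CL × MRT returns 116 L when MRT = 116/298 = 0.389 h. That MRT is back-calculated, because the documents state none. In two-compartment models with CL 298 L/h, Vdss 116 L and t½ 68.2 min, the theoretical CL × MRT is 116 L and CL/lambda_z is 489 L for each central volume tried (60, 80 and 100 L). The infusion correction matters: without subtracting half of the 1-hour infusion, the result is 298 × (0.389 + 0.5) = 265 L, 2.3 times too high.

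**5. Behaviour on the planned sampling times (illustration only).** Inputs: one noise-free adult-typical profile, 34.6 mg (20 × 1.73) over 1 h, with CL, Vdss and t½ as above. A central volume V1 of 65.5 L and intercompartmental clearance of 35 L/h give a Cmax of 107 ng/mL, the Table 1 value. The seven sampling times in footnote r of the Time and Events Schedule are 0, 0.5, 1, 1.083, 1.5, 2 and 3 h from the start of infusion.

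| AUC method | Points for slope | t½ (min) | CL/lambda_z (L) | CL × MRT (L) |
|---|---|---|---|---|
| Linear | last 2 | 55.8 | 420 | 142.7 |
| Linear | last 3 | 36.7 | 278 | 131.9 |
| Linear-up/log-down | last 2 | 55.8 | 435 | 150.6 |
| Linear-up/log-down | last 3 | 36.7 | 288 | 139.1 |

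The printed formula gives 0.0023–0.0036 per L. CL × MRT is 14–30% above the true 116 L (131.9/116 = 1.14; 150.6/116 = 1.30).

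**6. Sensitivity to V1.** Over V1 from 10 to 110 L, with the other inputs fixed, Cmax moves only from 101.9 to 108.0 ng/mL, inside Table 1's interval of 88.5–129, so Cmax hardly identifies V1. Over that range CL × MRT runs from 128.4 to 208.2 L (11–79% high) and CL/lambda_z from about 127 to 585 L. At V1 = 110 L the two nearly coincide (135–141 L against 127–138 L).

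**The case against.** The strongest reply is that nothing turns on the line. The analysis is assigned to the sponsor's PK guideline and to named software, so the printed expression is probably a descriptive gloss on a calculation done correctly elsewhere. VDss is not a named Phase 1 primary PK parameter (Sections 2.1 and 9.2.2 name Cmax, AUC, tmax and Cl). Sections 9.2.5, 9.3 and 11.5 plan a population model, and Section 9.3 names volume of distribution among its outputs. All of this stands, and it is why the point is minor. It does not make the rule right. The section says the listed parameters will be calculated, and if the software does something else, the reported value and the protocol disagree.

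A second reply is that the size of the gap between Vz and VDss depends on the inputs. That also stands. Section 9.2.5 itself quotes a terminal half-life of 0.51 h. With Table 1's CL that gives lambda_z = 0.693/0.51 = 1.359 /h and CL/lambda_z = 219 L, about 1.9 times 116 L rather than 4.2 times (mixing two sources). On the planned times the gap can nearly vanish for some central volumes. So 4.2 is not a forecast for this trial. The unit error is independent of these figures.

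A third reply is that the label and Table 1 both say steady state, so the intended quantity is clear. That favours keeping VDss, but the formula would still have to be replaced and not merely inverted.

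**Conclusion.** The formula is wrong as written. It returns a reciprocal volume, no other section supplies a valid rule, and an inversion in printing or in reading the PDF does not explain it, because the inverse is Vz. From Table 1, Vz and Vdss differ 4.2-fold for the 5-day regimen (489 L against 116 L).

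The unit error rests only on the definitions in Section 9.2.5. The litre figures rest on adult population estimates and, for the sampled profile, on an assumed central volume; none of them estimates an error in the pediatric results. Severity is minor: one descriptive PK parameter is affected, and no dose, MTD, sample size or efficacy conclusion.

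**What to change.** Correct the entry in Section 9.2.5 and in the PK analysis specification in one of two ways:

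- **(a) Keep VDss.** State VDss = CL × MRT, with MRT = AUMC(0–∞)/AUC(0–∞) minus half the infusion time (0.5 h for the 1-hour infusion). This keeps the quantity comparable with the adult Vdss in Table 1. It adds AUMC, MRT and AUC(0–∞) to the list, which the section's allowance for additional parameters already permits. The estimate may be biased upward on the planned times.
- **(b) Relabel.** Call the parameter Vz = CL/lambda_z, change label and formula together, and do not compare it with Table 1's Vdss. This adds no parameter but gives up a non-compartmental VDss, and Vz still depends on the terminal slope.

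Under either option, it would help to say that the exclusion in Section 11.5 for "concentration data not sufficient for PK parameter calculation" covers this volume. Section 9.2.3 tells sites with a single-lumen central line to "consider to only collect pre-infusion and post-infusion PK samples", and says that "the collection timepoints of PK samples may be optimized and if possible reduced for the Phase 2 portion of the study"; some children may therefore have no usable terminal slope. Naming the population-PK volume as the main volume estimate would also be reasonable, but the correction does not require it.

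The cost is one line of text. No sample, dose or endpoint changes.
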